4.1. Primary outcome

-Time until the resolution of the symptoms in the two study groups. Number of days from randomization visit to the first symptom-free day (score of 0 on the 8-point scale). Variable measured during the 21 days of follow-up.

4.2. Secondary outcomes

-Proportion of cases with deterioration in two or more points of the 8-point ordinal scale in the two study groups. Proportion of subject who reported an increase in disease severity of 2 or more points on the 8-point ordinal scale relative to the randomization visit.

-Proportion of cases that required hospitalization, use of supplemental oxygen > 24 hours, and admission to the ICU.

-Duration of hospitalization, use of supplemental oxygen and duration of stay in ICU in each arm of the study.

-Clinical state, using the 8-point ordinal scale, on days 2, 5, 8, 11, 15, and 21.

-Proportion of cases who develop fever (axillary temperature > 38°C or subjective feeling of fever) in each arm of the study and duration of fever. Number of days from the randomization visit to an axillary temperature <38°C.

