4.1.5.2. Secondary outcomes to be evaluated

- To determine the time to deterioration in two or more points of the 7-point ordinal scale in the two study groups.
- To determine the clinical state, using the 7-point ordinal scale, on days 2, 5, 8, 11, 15, and 21.
- The proportion of subjects requiring hospitalization, use of supplemental oxygen > 24 hours, admission to the ICU, or dying within 21 days in the two trial groups.
- The duration of supplemental oxygen in each arm of the study.
- The duration of hospitalization in each arm of the study.
- The duration of stay in the ICU in each arm of the study.
- The duration of fever (axillary temperature > 38C or subjective feeling of fever) in each arm of the study.
- Proportion of subjects who develop adverse events associated with the study drug.
- Proportion of subjects who required discontinuation of medication due to adverse events.

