4.3.3 Table of visits and follow-ups

| Visit number (V) | Screening | Randomization | Phone call 1 | Phone call 1 | Phone call 1 | Phone call 1 | Phone call 1 | Phone call 1 | Phone call 1 | Phone call 1 |
|---|------------|---------------|-----------------|-----------------|-----------------|-----------------|-----------------|-----------------|-----------------|-----------------|
| Study deadlines | SCR | D1 | D2 | D3 | D4 | D5 | D8 | D11 | D 15 | D 21 |
| Intervals (days) | | | | | | | ±1 | ±1 | ±1 | ±1 |
| Signed informed consent form | X | | | | | | | | | |
| Inclusion/exclusion criteria | X | X | | | | | | | | |
| Assignment of the research participant number | X | | | | | | | | | |
| Demographic Data | X | | | | | | | | | |
| Medical background check | | X | | | | | | | | |
| Weight | X | | | | | | | | | |
| Vital signs and pulse oximetry | | X | | | | | | | | |
| Calculation of NEWS -2 score: | | X | | | | | | | | |
| Collection of clinical data | | X | | | | | | | | |
| Urine sample to evaluate pregnancy | X | | | | | | | | | |

| | | | | | | | | | | |
|---|-----------------------|----------|----------|----------|----------|----------|----------|----------|----------|----------|
| Blood Sample to evaluate Hepatic enzymes ² | X ² | | | | | | | | | |
| Randomization | | X | | | | | | | | |
| Dispensing and initiating medication/placebo | | X | | | | | | | | |
| Evaluation of the 7-point ordinal scale | | X | X | X | X | X | X | X | X | X |
| Assessment of secondary outcomes - Pt. at home or hospitalized? - Has required oxygen? - Has required ICU? - Vital status - Persists with fever? | | X | X | | | X | X | X | X | X |
| Collection of Serious Adverse Events (SAE) | | | X | | | X | X | X | X | X |
| Pharmacotherapeutic Adherence | | X | | | | X | | | | |
| Remember the need to take the investigation product | | | X | X | X | X | | | | |
| Collect symptoms reported to the admin of the investigation product | | | X | X | X | X | X | X | X | X |
| Record of completion | | | | | | | | | | X |

¹ In the case of hospitalized research participants, the study staff will personally visit the subject and/or contact the physician in charge by telephone, and/or through the medical history will obtain the necessary information and thus be able to determine primary or secondary outcomes

² It will not be necessary to collect the liver enzyme sample if there is a recent result no more than 3 days prior to selection.

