6.2. Secondary outcomes

Secondary outcomes, hospitalization requirement, ICU or oxygen supplementation and deterioration in more than two points on the scale of clinical results will be analyzed through a Kaplan Meier estimate. Hazard ratio will be estimated by Cox proportional-hazard model. In addition, a logistic regression model in which each secondary outcome will be considered as the dependent variable (1: Event, 0: No event) and the intervention groups as the independent variable (1: ivermectin, 0: Placebo) will be used.

For each outcome, the odds ratio (OR) and its respective 95% CI will be reported. An OR > 1 is indicating favorable results in favor of placebo and an OR <1 in favor of ivermectin. In case of low frequency of individual outcomes, a combined variable will be created using need for hospitalization (general floor or ICU) and need for oxygen (by nasal cannula or mechanical ventilation) and will be analyzed using a logistic regression model reporting the OR with its 95% CI.

Evaluation of the effect of the treatment in each study visit using the 8-point ordinal scale will be estimated using the proportional OR with its respective 95% CI with an ordinal logistic regression. In this step, the 8-point ordinal scale will be inverted in its score, where 0 will correspond to death and 7 to a subject without symptoms. Thus, a proportional OR > 1 will indicate an effect in favor of ivermectin. The 95% confidence interval of the median difference in duration of fever and length of hospitalization or oxygen use will be estimated by bootstrap estimators.

6.3. Sensitivity Analysis and Modification of the Effect for the Primary outcome.

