6.5. Handling missing data

Primary outcome:

The primary outcome is expected to be available in all patients. In the event that the patient dies during follow-up, a censoring for the study will be considered until the time of last observation. If the patient is lost to follow-up, last report on the 8-point scale during follow-up will be considered as the outcome.

Covariates: If there are missing data in the variables needed to analyze for effect modification, and this may have an effect the primary outcomes of the study, then simple imputation will be performed using the median of the treatment group to which the observation belongs based on the information reported in the sample with complete data.

Secondary outcomes. Data will not be imputed. The percentage of missing data will be reported.

Summary of Changes in the Statistical Analysis Plan

1. Introduction:

The original primary outcome (time until worsening in 2 or more points in the 7-point ordinal scale) was replaced by the final primary outcome (time to resolution of symptoms)

2.2 Sample size calculation:

The original sample size was calculated to 400, in order to detect a hazard ratio in time to deterioration of 0.5 of ivermectin vs. placebo. The sample size remained 400 patients, after the primary endpoint was modified. However, the sample size increased to 476 due to 76 patients who were excluded from primary analysis (76 subjects who had errors in the label of the investigation product consecutively for three weeks)

4.1 primary outcome

The primary outcome was changed to Time until resolution of symptoms in the two study groups

4.2 secondary outcomes

The primary outcome became a secondary outcome. The ordinal scale changed from 7 to 8 points to include the score of 0.

The proportion of subjects who develop fever was added as an indirect marker of the antiviral capacity of the drug

6. Analysis Plan

The STATA version was updated to 16.0

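### SAP 4.2 counts fever by temperature or feeling but times it from randomisation to a temperature below 38°C, so felt-only and later-onset fevers get wrong durations

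*Supplement*

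**What the plan says.** In the current SAP (September 2020), section 4.2 lists "Proportion of cases who develop fever (axillary temperature > 38°C or subjective feeling of fever) in each arm of the study and duration of fever". The next sentence gives the time measure: "Number of days from the randomization visit to an axillary temperature <38°C". SAP 6.2 sets out the comparison: "The 95% confidence interval of the median difference in duration of fever and length of hospitalization or oxygen use will be estimated by bootstrap estimators". It does not say which patients enter that comparison. On missing values SAP 6.5 says "Secondary outcomes. Data will not be imputed".

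The current protocol (476 subjects), section 4.1.5.2, has "The duration of fever (axillary temperature > 38C or subjective feeling of fever) in each arm of the study". It applies the two-part fever definition to duration but gives no start or end.

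In the protocol's visit table (4.3.3), the row "Vital signs and pulse oximetry" is marked only at the randomisation visit, D1. The item "Persists with fever" is marked at D1, D2, D5, D8, D11, D15 and D21. Protocol 4.3.7 also lists fever among the symptoms asked about at every call: D2, 3, 4, 5, 8, 11, 15 and 21.

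**The concern.** A duration needs a start and an end that refer to the same state. Here a patient becomes a fever case through either of two routes, but leaves it through only one. Someone who feels feverish with a normal reading at randomisation is a case whose end criterion is already met. The outcome also covers patients who develop fever during follow-up, yet their clock starts at randomisation, before the fever exists.

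The protocol's summary of changes says fever duration was added as an indirect sign of antiviral activity. If its values do not measure how long patients were febrile, the median difference promised in SAP 6.2 cannot be read that way. Two analysts could also obtain different results from the same data.

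**Working it through.** The plan states no figure for fever duration (no expected value, power or alpha), so there is nothing to reproduce. The check applies the SAP rule to example histories.

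**Inputs from the documents.** Fever is a reading above 38°C or a felt fever (SAP 4.2). The clock starts at randomisation, D1. The stop is a reading below 38°C (SAP 4.2).

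**Assumptions.** Readings are daily: 38.6°C on days of measured fever and 37.2°C otherwise. The histories are hypothetical.

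**Formulas.**
- Target: number of days that meet the SAP's own fever definition.
- Reading A, the first low reading ends the count: (first day below 38°C) − 1.
- Reading B, the low reading after the fever is meant: (first day below 38°C after the last febrile day, measured or felt) − 1.

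| History | Target | Reading A | Reading B |
|---|---|---|---|
| Measured D1–4 | 4 | 5 − 1 = 4 | 5 − 1 = 4 |
| Felt only, D1–5 | 5 | 1 − 1 = 0 | 6 − 1 = 5 |
| Measured D6–10 | 5 | 1 − 1 = 0 | 11 − 1 = 10 |
| Measured D1–2, felt to D6 | 6 | 3 − 1 = 2 | 7 − 1 = 6 |
| Exactly 38.0°C on D1–4, not felt | 0 | 5 − 1 = 4 | undefined |

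Only the first history, measured fever present at randomisation with no felt tail, is scored correctly on both readings. Reading B rescues the two felt histories only because the felt part has been added to the stop, and the SAP sentence does not contain it. Even then, later-onset fever is counted from randomisation and gains 10 − 5 = 5 days without fever. The last row shows a small gap: exactly 38.0°C is neither fever nor resolution.

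**Can the stop be observed?** Staff vital signs are scheduled at D1 only, and no temperature row is marked for the calls. For inpatients the medical record may supply readings. For outpatients febrile at D1 no later reading is scheduled. With no imputation of secondary outcomes, their durations could be missing rather than short.

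**The case against.** The strongest reply is that this is a secondary outcome with no alpha or power attached. The primary analysis and the proportion with fever are untouched, and the protocol already applies the two-part definition to duration, so a sensible analyst would do the right thing. The first parts of that stand and limit the weight of the point. The last does not: the protocol gives no start or end, so it cannot override the SAP's explicit rule.

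A reader might go further than the documents allow in three ways.

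- **That every later-onset fever scores zero.** This needs the word *first* read into the SAP sentence. Otherwise such fevers are over-counted. They are wrong either way, but in opposite directions.
- **That temperature is never collected and the calls ask only whether fever persists.** Protocol 4.3.7 has fever asked about at every call. Each call completes a questionnaire whose fields are not shown, and an answer could rest on a home reading. What is supported is that no follow-up temperature measurement is scheduled.
- **That the comparison is biased toward no effect, or that both medians must be zero.** Zero medians would need at least half of the analysed patients in each arm to score 0. The documents give neither the share of felt-only or later-onset fevers nor the analysis set. If all randomised patients were analysed, those who never had fever could put the median at zero without this defect.

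**Conclusion.** The mismatch is present in the current SAP, and nothing elsewhere repairs it. As written, felt-only fever with a reading below 38°C at D1 scores 0 days, and a felt tail after measured fever is dropped (2 days instead of 6 in the example). Fever starting after D1 is either scored 0 or over-counted (0 or 10 days against 5). The stop criterion may be unobservable in outpatients.

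These sizes are for single example patients and rest on assumed daily readings. The direction and size of the effect on the arm comparison cannot be determined from the documents. The correction should be made because the rule gives wrong durations and the repair is cheap, but it concerns one secondary outcome and does not affect the trial's main conclusion.

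**What to change.** Rewrite the duration sentence in SAP 4.2 as follows.

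- **Start:** randomisation if the patient is febrile then, otherwise the first later fever report.
- **Stop:** the first subsequent contact with neither a reading above 38°C nor a felt fever.
- **Source:** the "Persists with fever" item together with the fever symptom item asked at every call, which adds D3 and D4.
- **Gaps:** treat the stop as interval-censored between calls, or assign it by a stated convention. Say the same for the onset of new fever.
- **Censoring:** state how fever continuing at D21, loss to follow-up and death are censored.
- **Boundary:** assign exactly 38.0°C to one side.
- **Analysis set:** state who enters the median comparison in SAP 6.2, and report fever present at randomisation separately from new-onset fever. Which of these is the main set is a secondary choice.

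This needs SAP wording only, provided the call forms hold the fever answers as the protocol describes.

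The cost is precision. Calls are daily from D2 to D5, then 3, 3, 4 and 6 days apart (D5 to D8, D11, D15, D21), before the ±1-day windows. In the example of felt fever on D1–5, the last febrile contact is D5 and the first clear one is D8. The duration is then known only to exceed 5 − 1 = 4 days and be at most 8 − 1 = 7. The D6–10 fever is reported only at D8 and is clear at D11, so it spans 11 − 8 = 3 days by reports and at most 11 − 5 = 6. These values are coarse, but they measure the fever that the SAP defines.

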4.3. Safety outcomes

-Proportion of subjects who develop adverse events and serious adverse events associated with the study drug: patients who during follow-up report episodes of uncontrollable

tremor, dizziness, loss of appetite, nausea, vomiting, stomach pain, bloating, diarrhea, constipation, weakness, drowsiness, chest discomfort, edema (face, arms, hands, feet, ankles or calves), pain and swelling in the joints, painful and swollen glands in the neck, armpit or groin, fast heartbeat, eye pain, blurred vision, redness or tearing, swelling of the eyes or the eyelids, abnormal sensation in the eyes, fever, blistering or peeling of the skin, rash, hives, and itching.

-Proportion of subjects who required discontinuation of medication due to adverse events.

5. Study population and subgroup analysis

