Another possible mechanism of action would be by enhancing the immune system as has been described for onchocerciasis and psoriasis in humans.²⁹⁻³³

The half-life of the D11AX22 (Ivermectin) molecule in plasma is at least 16 hours. It is absorbed mainly in the intestine and passes into the bloodstream after being administered orally, reaching a therapeutic peak 4 hours after oral administration. It is metabolized in the liver and its metabolites are almost exclusively excreted in the feces, less than 1% of the dose is excreted in the urine.¹⁴ The recommended therapeutic doses as antiparasitic vary between 0.05 and 0.40 mg/kg without undesirable effects or risk to human life; When administered in doses of 0.20 mg/kg, the maximum plasma concentrations reached after four hours are 20 ng/ml, while toxic doses are on the order of 6.6 to 8.6 mg/kg, which can lead to vomiting, blurred vision, mydriasis, ataxia, tremor, and coma. Lethal doses are on the order of 24 mg/kg. No contraindications for its use in humans or negative effects on reproduction or pregnancy have been described, and at least 250 million people in the world have received different doses of this molecule. All of the above allows us to consider the D11AX22 (Ivermectin) molecule as a very safe drug in humans, in whom low toxicity has been seen, unlike other animal species.³⁴

Thus, taking into account the in vitro inhibitory capacity against different types of viruses, including SARS CoV2, the encouraging clinical data in humans with COVID 19, the extensive experience in humans that has demonstrated safety using this drug for other pathologies, and the extensive use of the molecule D11AX22 (ivermectin) by this group of investigators,³⁵⁻³⁹ There is sufficient rationale to evaluate its use in adults with mild COVID-19 illness.

Given the high morbidity that this disease generates, and the urgent need to find strategies that allow us to reduce disruption in our current lifestyle through safe measures, we propose a double-blind, randomized, placebo-controlled clinical trial to evaluate the efficacy of the D11AX22 (ivermectin) molecule in adults with mild COVID-19 disease.

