4.1.4. Intervention

The subjects will be divided into 2 groups, which will be randomized 1: 1

Group 1: Study participants over 18 years of age with mild illness due to SARS CoV2 / COVID 19 who consult at participating institutions in Valle del Cauca and are randomized to receive ivermectin, once a day for 5 days.

Treatment name: D11AX22 (Ivermectin) Molecule

Drug Name: Ivermectin

Presentation: oral drops in suspension 6 mg/ml.

Route of Administration: Oral

Primary container: 5mL bottle

Volume to be administered: Depends on the subject's weight

Dose: 300 mcg/kg/day

Storage conditions on the label: Room temperature

Indications for administration: It is recommended to take on an empty stomach, preferably a single dose on an empty stomach, with water

Serious interactions: Warfarin, erdafitinib, quinidine

These doses or higher have been used previously and for longer periods of time for other pathologies demonstrating adequate tolerance.^{37,40,41}

Group 2: Study participants over 18 years of age with mild illness due to SARS CoV2 / COVID 19 who consult at participating institutions in Valle del Cauca and are randomized to receive a placebo.

Treatment name: Placebo

Drug Name: Placebo

Presentation: solution

Route of Administration: Oral

Primary container: 5mL bottle

Volume to be administered: Depends on the subject's weight

Dose: same volume that would be administered of Ivermectin to maintain the blind

Storage conditions on the label: Room temperature

Indications for administration: Same as ivermectin.

The active drug and the placebo will be re-labeled to keep study participants and study members blinded. The only person not blinded to the study procedures will be the pharmaceutical chemist who will randomize the study participants.

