6.4. Safety analysis

This analysis will be carried out on an exploratory basis and the frequency and detailed description of each adverse event will be reported.

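### SAP 4.3 defines both adverse events and serious adverse events by one closed list of patient-reported symptoms, with no seriousness criterion, which is narrower than the protocol and SAP 6.4

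*Supplement*

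**What the plan says.** SAP 4.3 names one outcome for two kinds of event and defines it after a colon: "adverse events and serious adverse events associated with the study drug: patients who during follow-up report episodes of uncontrollable" tremor, then a run of more than 20 further symptoms that closes with "fever, blistering or peeling of the skin, rash, hives, and itching". No item for other events follows. The SAP contains no second definition of a serious adverse event, no seriousness criterion and no method for judging association with the drug.

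SAP 6.4, the only section on safety analysis, reads: "This analysis will be carried out on an exploratory basis and the frequency and detailed description of each adverse event will be reported".

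The protocol (current version, with 476 subjects) handles the same matter in four places:

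- Section 4.1.5.2 lists, among the secondary outcomes, the proportion with adverse events associated with the drug. It gives no symptom list.
- Section 4.3.7 has a symptom questionnaire asked on eight calls. It is close to the SAP list but includes an item for other symptoms. The section then compares the proportion with adverse events between arms.
- Table 4.3.3 has a separate row, "Collection of Serious Adverse Events (SAE"), marked at D2, D5, D8, D11, D15 and D21, with no symptom restriction.
- Section 2 describes signs of toxic doses, "which can lead to vomiting, blurred vision, mydriasis, ataxia, tremor, and coma".

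**The concern.** A serious adverse event is normally identified by its seriousness, whatever the symptom. SAP 4.3 identifies it by whether the patient reports something on a list. Two consequences follow from the wording.

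First, a serious event that produces no listed complaint falls outside the proportion, even though the protocol collects it. Second, adverse and serious adverse events share one definition, so the SAP gives no rule for telling them apart. A patient with mild itching and a patient with a listed symptom and a life-threatening event meet the same definition.

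Safety is one of the protocol's specific objectives (3.2). Two analysts with the same data could report different serious-event counts: one following 4.3 literally, the other using the dedicated collection row. Much of the list (fever, weakness and diarrhoea, for example) can come from COVID-19 itself. The 4.3 proportion may therefore be made up largely of illness symptoms while saying little about serious events.

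**Working it through.** The plan states no figure on this point, so there is none to reproduce. The check sets the texts side by side, with a little arithmetic for dose context.

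**1. Scope of each definition**

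| Place | What counts | Open to events off the list? | Seriousness separated? |
|---|---|---|---|
| SAP 4.3 | Patient reports a listed symptom | No | No |
| SAP 6.4 | Each adverse event | Not limited there, but no definition given | No |
| Protocol 4.1.5.2 | Adverse events associated with the drug | Yes | No |
| Protocol 4.3.7 | Listed symptoms and other symptoms | Yes | No |
| Protocol table 4.3.3 | Serious adverse events, own row | Yes | Yes |

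SAP 4.3 is the only closed entry, and it is the one that defines the reported proportion.

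**2. Match of the protocol's toxic-dose signs to the SAP list**

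- On the list: vomiting, blurred vision, tremor (3 of 6).
- Not on the list: mydriasis, ataxia, coma (3 of 6).

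The nearest listed items are dizziness and drowsiness.

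**3. What the SAP 4.3 rule does with a recorded serious event**

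- Off-list event, no listed symptom ever reported: the patient is not in the proportion.
- Off-list event, listed symptom also reported: the patient is in the proportion because of that symptom, and the serious event is not identified.
- Serious event that is itself a listed symptom: the patient is in the proportion but cannot be told from a mild case.

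In none of the three does the rule yield a correct serious-event proportion.

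**4. Dose context for the illustration**

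Inputs: "Dose: 300 mcg/kg/day" given "once a day for 5 days" (protocol 4.1.4), and "toxic doses are on the order of 6.6 to 8.6 mg/kg" (protocol section 2).

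- Daily dose: 0.3 mg/kg. Ratios: 6.6 / 0.3 = 22 and 8.6 / 0.3 = 28.7.
- Five-day total: 5 × 0.3 = 1.5 mg/kg. Ratios: 6.6 / 1.5 = 4.4 and 8.6 / 1.5 = 5.7.

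The doses that the protocol ties to these signs are about 22 to 29 times the daily dose and 4.4 to 5.7 times the course total. The three missing signs show how the list and the protocol diverge. They do not show that such events are expected in this trial.

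**The case against.** The strongest reply is that the rest of the plan already covers these events. Serious events are collected at six contacts without a symptom filter. For hospitalised participants, the footnote to table 4.3.3 and section 4.3.5 allow information from the physician or the medical record. That footnote covers the secondary outcomes, and the adverse-event proportion is one of them, so the data do not depend on an unconscious patient reporting anything. SAP 6.4 reports every adverse event. A patient with an off-list event also enters the proportion if any one of more than 20 listed symptoms, many common in COVID-19, is reported on any of eight calls.

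Most of this stands, and it rules out three stronger readings that a reader might infer:

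- *Off-list toxicity would go uncounted, or the trial could report no serious events on ivermectin.* Not supported: the events are collected, and 6.4 provides for their frequency and description.
- *A number of missed cases can be calculated.* Not supported: the documents give no event rate, and any such sum would have to assume that affected patients report no listed symptom at all.
- *The list leaves out the drug's most characteristic toxicity.* Not supported: the protocol does not rank the signs, and tremor, itself a neurological sign, is the first item on the list.

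The reply does not remove the conflict over the proportion. SAP 6.4 is labelled exploratory, offers no definition of its own and does not alter the 4.3 outcome. The separate collection row confirms that the data will exist; SAP 4.3 gives no rule for counting them.

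**Conclusion.** The point holds as an inconsistency in an outcome definition. SAP 4.3 states a rule that would give a wrong serious-adverse-event proportion, and that rule is narrower than protocol 4.1.5.2, 4.3.7 and table 4.3.3, and than SAP 6.4. A recorded serious event outside the list would not enter the 4.3 proportion unless a listed symptom was also reported, and would not be identified there as serious. It would still be collected and could be described under 6.4.

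The size can be given only in kind: 3 of the 6 toxic-dose signs named in the protocol are off the list, and any off-list serious event in either arm is affected, whatever its cause. The number of patients involved cannot be derived from the documents.

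The conclusion rests on reading 4.3 literally, with the words after the colon as the definition. If the authors meant the list as examples, the intention is sound but the text does not say so. One further caution: in protocol 4.3.7 the item for other symptoms stands in the middle of the list, so its status as an open question should be made explicit.

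**What to change.** In SAP 4.3, replace the single definition with two outcomes:

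- **Serious adverse events:** every serious adverse event recorded at the scheduled collections (D2, D5, D8, D11, D15, D21) or taken from the physician or medical record, whatever the symptom, tabulated by arm.
- **Adverse events:** the existing list, described as solicited symptoms, plus the protocol's item for other symptoms, tabulated by arm.

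The cost is a wording change to the SAP, using data the protocol already collects. It needs no new visits, questions or procedures, and no change to dosing or clinical management. One small downside should be expected: the reported serious-event count may rise, because COVID-19 admissions recorded as serious events will be included. Tabulation by arm lets the reader judge those against placebo.
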